5.2.5 Vital signs

Vital signs will be measured at the times specified in the study plans (Table 1) and recorded in the eCRF. However, the Investigator reserves the right to add extra assessments if there are any abnormal findings or for any other reason the Investigator feels meets this requirement.

5.2.5.1 Pulse and blood pressure

Pulse and blood pressure will be measured at the times specified in the study plans (Table 1).

5.2.5.2 Body temperature

Body temperature will be measured at the times specified in the study plans using a semi-automatic body temperature recording device.

5.2.6 Other safety assessments (Not applicable)

5.3 Other assessments (Not applicable)

5.4 Pharmacokinetics (Not applicable)

5.5 Pharmacodynamics (Not applicable)

5.6 Pharmacogenetics (Not applicable)

5.7 Biomarker analysis

The subject's consent to the use of donated biological samples is mandatory. Biological samples (e.g., archived tumour samples and cfDNA) will be collected and may be analysed for exploratory biomarkers to assess correlations with disease activity, effects of study drug, clinical outcomes and toxicity.

5.7.1 Storage, re-use and destruction of biological samples

Samples will be stored for a maximum of 15 years from the date of the Last Subject's Last Visit, after which they will be destroyed. The results of this biomarker research will be reported either in the Clinical Study Report itself or as an addendum, or separately in a scientific report or publication.

5.7.2 Labelling and shipment of biological samples

The Principal Investigator ensures that samples are labelled and shipped appropriately.

5.7.3 Chain of custody of biological samples

A full chain of custody is maintained for all samples throughout their lifecycle. The Principal Investigator keeps full traceability of collected biological samples from the subjects while in storage at the centre until shipment or disposal (where appropriate) and keeps documentation of receipt of arrival. The sample receiver keeps full traceability of the samples while in storage and during use until used or disposed of or until further shipment and keeps documentation of receipt of arrival. The sponsor keeps oversight of the entire life cycle through internal procedures, monitoring of study

sites and auditing of external laboratory providers. Samples retained for further use should be documented and stored during the entire life cycle.

5.7.4 Withdrawal of Informed Consent for donated biological samples

If a subject withdraws consent to the use of donated biological samples, the samples will be disposed of/destroyed, and the action documented. If samples are already analysed, the sponsor is not obliged to destroy the results of this research.

The Principal Investigator:

- Ensures subjects' withdrawal of informed consent to the use of donated samples is notified immediately
- Ensures that biological samples from that subject, if stored at the study site, are immediately identified, disposed of /destroyed, and the action documented
- Ensures the laboratory(ies) holding the samples is/are informed about the withdrawn consent immediately and that samples are disposed of/destroyed, the action documented and the signed document returned to the study site
- Ensures that the subject and the sponsor are informed about the sample disposal.

The sponsor ensures the central laboratory(ies) holding the samples is/are informed about the withdrawn consent immediately and that samples are disposed of/destroyed and the action documented and returned to the study site.

6. SAFETY REPORTING AND MEDICAL MANAGEMENT

The Principal Investigator is responsible for ensuring that all staff involved in the study are familiar with the content of this section.

6.1 Definition of adverse events

An adverse event is the development of an undesirable medical condition or the deterioration of a pre-existing medical condition following or during exposure to a pharmaceutical product, whether or not considered causally related to the product. An undesirable medical condition can be symptoms (e.g., nausea, chest pain), signs (e.g., tachycardia, enlarged liver) or the abnormal results of an investigation (e.g., laboratory findings, electrocardiogram). In clinical studies, an AE can include an undesirable medical condition occurring at any time, including run-in or washout periods, even if no study treatment has been administered. The term AE is used to include both serious and non-serious AEs.

6.2 Definitions of serious adverse event

A serious adverse event is an AE occurring during any study phase (i.e., treatment, follow-up), that fulfils one or more of the following criteria:

- Results in death
- Is immediately life-threatening
- Requires in-patient hospitalisation or prolongation of existing hospitalisation
- Results in persistent or significant disability/incapacity or substantial disruption of the ability to conduct normal life functions
- Is a congenital abnormality or birth defect
- Is an important medical event that may jeopardise the subject or may require medical intervention to prevent one of the outcomes listed above.

The causality of SAEs (their relationship to all study treatment/procedures) will be assessed by the investigator(s) and communicated to AstraZeneca in accordance with the agreed process.

6.3 Recording of adverse events

6.3.1 Time period for collection of adverse events

Adverse Events will be collected from time of signature of informed consent, enrolment throughout the treatment period and including the 30-day follow-up period. SAEs will be recorded from the time of informed consent.

6.3.2 Follow-up of unresolved adverse events

Any AEs that are unresolved at the subject's last visit in the study are followed up by the Investigator for as long as medically indicated, but without further recording in the CRF. The sponsor retains the right to request additional information for any subject with ongoing AE(s)/SAE(s) at the end of the study, if judged necessary.

6.3.3 Variables

The following variables will be collect for each AE;

- AE (verbatim)
- The date when the AE started and stopped
- Whether the AE is serious or not

- Investigator causality rating against the Investigational Product (yes or no), comparator/combination drug (yes/no)
- Action taken with regard to investigational product/ comparator/combination agent
- Outcome.

In addition, the following variables will be collected for SAEs:

- Date AE met criteria for serious AE
- Date Investigator became aware of serious AE
- AE is serious due to
- Date of hospitalisation
- Date of discharge
- Probable cause of death
- Date of death
- Autopsy performed
- Causality assessment in relation to Study procedure(s)
- Causality assessment in relation to Other medication
- Description of AE.

It is important to distinguish between serious and severe AEs. Severity is a measure of intensity whereas seriousness is defined by the criteria in Section6.2 . An AE of severe intensity need not necessarily be considered serious. For example, nausea that persists for several hours may be considered severe nausea, but not a SAE unless it meets the criteria shown in Section0. On the other hand, a stroke that results in only a limited degree of disability may be considered a mild stroke but would be a SAE when it satisfies the criteria shown in Section 6.2.

6.3.4 Causality collection

The Investigator will assess causal relationship between Investigational Product and each Adverse Event. For SAEs causal relationship will also be assessed for other medication and study procedures. Note that for SAEs that could be associated with any study procedure the causal relationship is implied as 'yes'.

6.3.5 Adverse events based on signs and symptoms

All AEs spontaneously reported by the subject or revealed by observation will be collected and recorded in the CRF. When collecting AEs, the recording of diagnoses is preferred (when possible) to recording a list of signs and symptoms. However, if a diagnosis is known and there are other signs or symptoms that are not generally part of the diagnosis, the diagnosis and each sign or symptom will be recorded separately.

6.3.6 Adverse events based on examinations and tests

Deterioration as compared to baseline in protocol-mandated laboratory values, vital signs should only be reported as AEs if they fulfil any of the SAE criteria or are the reason for discontinuation of treatment with the investigational product.

If deterioration in a laboratory value/vital sign is associated with clinical signs and symptoms, the sign or symptom will be reported as an AE and the associated laboratory result/vital sign will be considered as additional information. Wherever possible the reporting Investigator uses the clinical, rather than the laboratory term (e.g., anaemia versus low haemoglobin value). In the absence of clinical signs or symptoms, clinically relevant deteriorations in non-mandated parameters should be reported as AE(s). Any new or aggravated clinically relevant abnormal medical finding at a physical examination as compared with the baseline assessment will be reported as an AE.

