2.2 Secondary objectives

Secondary Objectives Outcome Measure

To evaluate the safety and tolerability of osimertinib AEs/SAEs as defined by NCI CTCAE version 4.0

To evaluate progression-free survival (PFS) PFS as defined by RECIST version 1.1

To evaluate overall survival (OS)

To evaluate the efficacy based on subtypes of EGFR exon 20 insertion mutation

To evaluate PFS based on subtypes of EGFR exon 20 insertion mutation

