5.2 Safety assessments

5.2.1 Laboratory safety assessments

Blood and urine samples for determination of clinical chemistry, haematology, and urinalysis will be taken at the times indicated in the Study Plan. The date, time of collection and results (values, units and reference ranges) will be recorded on the appropriate eCRF. The clinical chemistry, haematology and urinalysis will be performed at a local laboratory at or near to the Investigator site. Sample

tubes and sample sizes may vary depending on laboratory method used and routine practice at the site.

The following laboratory variables will be measured:

Table 2 Laboratory Safety Variables

Haematology/Haemostasis (whole blood)		Clinical Chemistry (serum or plasma)
B-Haemoglobin (Hb)	S/P-Creatinine	
B-Leukocyte count	S/P-Bilirubin, total	
B-Leukocyte differential count (absolute count)		S/P-Alkaline phosphatase (ALP)
B-Platelet count	S/P-Aspartate transaminase (AST)	
	S/P-Alanine transaminase (ALT)	
Urinalysis (dipstick)	S/P-Albumin	
U-Hb/Erythrocytes/Blood	S/P-Potassium	
U-Protein/Albumin	S/P-Calcium, total	
U-Glucose	S/P-Sodium	
	S/P-Creatine kinase (CK)	

The Investigator should make an assessment of the available results with regard to clinically relevant abnormalities. The laboratory results should be signed and dated and retained at centre as source data for laboratory variables. For information on how AEs based on laboratory tests should be recorded and reported, see Section.

NB. In case a subject shows an AST or ALT $\geq 3 \times \text{ULN}$ or total bilirubin $\geq 2 \times \text{ULN}$ please refer to Appendix C 'Actions required in cases of combined increase of Aminotransferase and Total Bilirubin – Hy's Law', for further instructions.

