6.7 Management of IP related toxicities

Dose adjustment for adverse events should be in accordance with the following table:

Table 3. AZD9291 dose adjustment information for adverse reactions

Target Organ	Adverse Reactiona	Dose Modification
Pulmonary	ILD/Pneumonitis	Permanently discontinue AZD9291
Cardiac	QTc interval greater than 500 msec on at least 2 separate ECGs	Withhold AZD9291 until QTc interval is less than 481 msec or recovery to baseline if baseline QTc is greater than or equal to 481 msec, then restart at a reduced dose (40 mg). QTc interval prolongation with signs/symptoms of serious arrhythmia Permanently discontinue AZD9291
Other	Grade 3 or higher adverse reaction	Withhold AZD9291 for up to 3 weeks If Grade 3 or higher adverse reaction improves to Grade 0-2 after withholding of AZD9291 for up to 3 weeks AZD9291 may be restarted at the same dose (80 mg) or a lower dose (40 mg) Grade 3 or higher adverse reaction that does not improve to Grade 0-2 after withholding for up to 3 weeks Permanently discontinue AZD9291

a Note: The intensity of clinical adverse events graded by the National Cancer Institute (NCI) Common Terminology Criteria for Adverse Events (CTCAE) version 4.0.

If a patient experiences a CTCAE grade 3 or higher and/or unacceptable toxicity (any grade), where the clinician considers the event of concern to be specifically associated with AZD9291 (and not attributable to the disease or disease-related processes for which patient is being treated), dosing will be interrupted and supportive therapy administered as required in accordance with local practice/guidelines. Detailed information on the clinical management of events may be found in Appendix B, "Guidance for the Management of Adverse Events in Studies using 80mg AZD9291."

Patients with QTc prolongation (i.e., confirmed QTc prolongation to >500 msec absolute or a > 60

msec increase from baseline) should have AZD9291 treatment interrupted and regular ECGs performed until resolution to baseline.

If the toxicity resolves or reverts to \leq CTCAE grade 2 within 3 weeks of onset, treatment with AZD9291 may be restarted at the same dose (80 mg, daily) or a lower dose (40 mg, daily) using the rules below for dose modifications (Table 4). There will be no individual modifications to dosing schedule in response to toxicity, only potential dose reduction or dose interruption.

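### Laboratory toxicity without symptoms that interrupts or reduces dosing and then recovers is not an adverse event under section 6.3.6, so it drops out of the safety outcome

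*Combined protocol and SAP*

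**What the plan says.** Section 6.3.6 sets three rules for findings from tests.

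- For deteriorations from baseline in protocol-mandated laboratory values and vital signs, the rule is that they "should only be reported as AEs if they fulfil any of the SAE criteria or are the reason for discontinuation of treatment". Dose interruption, dose reduction and CTCAE grade are not mentioned.
- If such a deterioration comes with symptoms, "the sign or symptom will be reported as an AE and the associated laboratory result/vital sign will be considered as additional information".
- Without symptoms, "clinically relevant deteriorations in non-mandated parameters should be reported as AE(s".

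The mandated panel (section 5.2.1, Table 2) includes haemoglobin, leukocyte differential, platelets, creatinine, bilirubin, AST, ALT and CK.

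Section 6.1 says that an AE can take the form of "the abnormal results of an investigation (e.g., laboratory findings, electrocardiogram". The secondary safety objective in section 2.2 reads "To evaluate the safety and tolerability of osimertinib AEs/SAEs as defined by NCI CTCAE version 4.0", and no laboratory outcome is listed beside it. For a grade 3 or higher adverse reaction, Table 3 in section 6.7 says "Withhold AZD9291 for up to 3 weeks". If the reaction improves to grade 0-2 in that time, "AZD9291 may be restarted at the same dose (80 mg) or a lower dose (40 mg". Permanent discontinuation has its own entries in the same table.

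**The concern.** The reporting rule in 6.3.6 and the toxicity rule in 6.7 draw the line in different places. Under 6.7, dosing is interrupted when the clinician attributes a grade 3 or higher event, or an unacceptable toxicity of any grade, to the study drug. Under 6.3.6, the same event is not an AE if it is a mandated laboratory change without symptoms, is not serious and does not end treatment. The protocol can thus manage an event as a drug-related adverse reaction that it does not count as an adverse event.

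At stake is how tolerability is described. Toxicity that changes dosing but can be managed is a large part of what a tolerability summary should show, and a summary built on AEs and SAEs would omit the laboratory part of it. No decision rule in the study uses an AE rate, so the effect is on description and not on the test of response.

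**Working it through.** The plan states no figure on this point, so there is none to reproduce. The check sets the sections side by side and then sizes the gap.

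**Step 1: does a hold count as discontinuation?** Section 6.3.6 names only discontinuation of the investigational product. Table 3 and the text of 6.7 use separate terms for withholding, interrupting, reducing and permanently discontinuing. A hold followed by restart at the same or a lower dose does not meet the 6.3.6 condition.

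**Step 2: which cases still enter as AEs or SAEs?**

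- Cases with symptoms: the symptom is reported (6.3.6).
- Combined transaminase and bilirubin elevation: may be an SAE (6.3.7).
- Cases that the investigator judges to be an important medical event: SAE (6.2).
- Grade 3 or higher toxicity not improved to grade 0-2 within 3 weeks: permanent discontinuation (Table 3), hence reportable.
- QTc-driven holds: 6.3.6 names laboratory values and vital signs, not ECGs, so these are not clearly affected.

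What remains is the asymptomatic, non-serious laboratory toxicity that leads to a hold or reduction and recovers.

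**Step 3: is that remainder captured elsewhere?**

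- Laboratory "results (values, units and reference ranges) will be recorded on the appropriate eCRF" (5.2.1).
- Dose interruptions and reductions are to be recorded (7.2), with no stated requirement to give a reason.
- Action taken with study drug is listed as a variable collected for each AE (6.3.3), and causality is assessed for each AE (6.3.4). Neither is required for an event that is not an AE.
- Section 8.2 plans general descriptive statistics. No CTCAE-graded laboratory summary is specified, and section 8.1 refers to a SAP only on condition that one exists.

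The raw data are kept. The attribution, and the link between the laboratory event and the dose change, have no required record.

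**Step 4: size.** Input: up to N = 30 patients dosed (8.2). One omitted patient changes a patient-level rate by at most

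1/N = 1/30 = 0.033, or 3.3 percentage points.

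This full amount applies to the grade 3 or higher AE rate only if the omitted event was grade 3 or higher and the patient has no other AE of that grade. Otherwise the change for that patient is zero.

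The documents give no rate of such events. For scale only, let q be an assumed share of patients affected, independently of one another. The expected number omitted is 30q, and the chance of at least one omission is 1 − (1 − q)^30.

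| Assumed q | Expected number omitted | Chance of at least one |
|---|---|---|
| 2% | 0.6 | 45% |
| 5% | 1.5 | 79% |
| 10% | 3.0 | 96% |
| 20% | 6.0 | 99.9% |

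**The case against.** The strongest defence is that the split in 6.3.6 is deliberate. Mandated results already have their own data stream on the eCRF, and the investigator must assess them for clinically relevant abnormalities (5.2.1). Non-mandated tests have no such stream and would be lost without an AE entry. On this view the rule avoids duplicate entries, and dated laboratory values can be matched to dated dose changes. This stands as a reason for the asymmetry. It also means that graded laboratory counts can be produced without changing AE collection. It does not restore the clinician's attribution, which 6.7 relies on when dosing is interrupted.

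Second, 6.1 is permissive: it says what an AE can be, and a specific rule may narrow it. This also stands, so the point does not rest on a contradiction with 6.1. It rests on 6.3.6 read with 6.7 and 2.2.

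Third, discontinuation might be read to include temporary stops, since the protocol sometimes adds the word permanently. That reading does not fit 6.7, which has separate words for temporary holds.

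Three stronger readings are tempting, and the documents do not support them:

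- **That every grade 3-4 laboratory event is excluded.** The routes in step 2 bring many of them back in.
- **That a dose hold has no recorded cause.** The CRF is not among the documents, so its dosing page may ask for a reason. What can be said is that the protocol does not require one.
- **That the grade 3 or higher AE rate is understated by 3 to 17 points.** This takes 1 to 5 affected patients out of 30 (5/30 = 16.7%). That count has no source in the documents, and the arithmetic assumes that none of those patients has another AE of that grade.

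**Conclusion.** The point holds in a narrow form and is worth an amendment. As written, 6.3.6 keeps asymptomatic, non-serious mandated laboratory toxicity that leads to a hold or reduction and recovers out of the AE/SAE safety outcome, although 6.7 can manage it as a grade 3 or higher adverse reaction. This follows from a stated rule and does not depend on any assumed rate.

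The size cannot be fixed from the documents. The bound is 3.3 percentage points on the grade 3 or higher AE rate for each omitted patient, given 30 treated patients and no other grade 3 or higher AE in that patient. The table of assumed q shows only that at least one omission is more likely than not if 5% or more of patients are affected. The primary response analysis is not touched.

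**What to change.** In section 6.3.6, add to the two existing conditions that a deterioration in a mandated laboratory value or vital sign is also an AE when it is the reason for interrupting or reducing the study drug. This brings 6.3.6 into line with 6.7, and the causality and action-taken items in 6.3.3 and 6.3.4 then apply without further change.

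In the safety analysis, add a table of worst CTCAE laboratory grade per patient, built from values already on the eCRF. The table alone would restore the graded counts but not the attribution, so both changes are needed.

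The dosing rules in 6.7 stay as they are. The cost is one sentence, one table, a few extra AE entries and a slightly higher reported AE rate.

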6.3.7 Hy's Law

Cases where a subject shows elevations in liver biochemistry may require further evaluation and occurrences of AST or ALT $\geq 3 \times \text{ULN}$ together with total bilirubin $\geq 2 \times \text{ULN}$ may need to be reported as SAEs. Please refer to Appendix for further instruction on cases of increases in liver biochemistry and evaluation of Hy's Law.

6.3.8 Disease progression

Disease progression can be considered as a worsening of a subject's condition attributable to the disease for which the investigational product is being studied. It may be an increase in the severity of the disease under study and/or increases in the symptoms of the disease. The development of new, or progression of existing metastasis to the primary cancer under study should be considered as disease progression and not an AE. Events, which are unequivocally due to disease progression, should not be reported as an AE during the study.

6.3.9 New cancers

The development of a new primary cancer should be regarded as an AE and will generally meet at least one of the serious criteria (see Section 6.4.2). New primary cancers are those that are not the primary reason for the administration of the study treatment and have developed after the inclusion

of the patient into the study. They do not include metastases of the original cancer. Symptoms of metastasis or the metastasis itself should not be reported as an AE/SAE, as they are considered to be disease progression.

6.3.10 Lack of efficacy

When there is deterioration in the condition for which the study treatment(s) is being used, there may be uncertainty as to whether this is lack of efficacy or an AE. In such cases, unless the Sponsor or the reporting physician considers that the study treatment contributed to the deterioration of the condition, or local regulations state to the contrary, the deterioration should be considered to be a lack of efficacy and not an AE.

